#### **Unfavourable**

A patient's outcome will be classified as **unfavourable** if:

- They are discontinued from their allocated study treatment and subsequently restarted on a different MDR-TB regimen.
- 2. Treatment is extended beyond the scheduled end of treatment for any reason other than making up days when no treatment was given (missed treatment) for a maximum of eight weeks. A maximum of 14 days of extra treatment (irrespective of reason) is acceptable before it is classified as treatment extension. In addition, if the intensive phase of treatment has been extended for delayed sputum conversion (maximum 8-week extension permitted) the scheduled end of treatment will also be extended by the same amount, in accordance with Section 7.3.2.
- 3. They are restarted on any MDR-TB treatment after the scheduled end of treatment, but before 132 weeks after randomisation for Stage 1 and before 76 weeks after randomisation for Stage 2.
- 4. They change their allocated study treatment for any reason other than (1) the replacement of a single drug\* or (2) for patients allocated to Regimen A when the change is as a result of changes in local guidelines and not related to any change in the patient's circumstances or condition.
- 5. Bedaquiline is started where the allocated regimen did not originally contain that drug (Regimen A or B)
- 6. A second line injectable agent is started in Regimen C.
- 7. A drug from the class of nitroimidazoles or linezolid is started.
- 8. They die at any point during treatment or follow-up.
- 9. At least one of their last two culture results, from specimens taken on separate occasions, is positive.
- 10. They do not have a culture result at Week 76 or thereafter for the Stage 1 comparison, or within the Week 76 window for the Stage 2 comparison.

11. The failure or recurrence specimen at or before the Week 76 window was a different strain to their randomisation specimen, i.e. re-infection (the Stage 2 comparison only).

Starting a single drug is not considered to be a substantial change to the regimen and therefore does not result in an unfavourable outcome, with the exception of adding bedaquiline (in Regimen A or B), a second-line injectable in Regimen C or a drug from the class of nitroimidazoles or linezolid (in any regimen).

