3 PRIMARY OUTCOME

3.1 Primary analysis Week 76 window

The Week 76 window is defined as the time period from six weeks before 76 weeks since randomisation to six weeks after 76 weeks since randomisation, i.e. from Week 70 to Week 82.

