3.1.1 Extension of visit window due to the COVID-19 pandemic

The end dates of the Week 76 window will be extended for any Stage 2 patients whose Week 76 appointment is scheduled to occur during the COVID-19 pandemic and did not occur due to restrictions on movement, unacceptable risk of exposure to COVID-19 in connection with the scheduled visit, or any other reason related to the pandemic. For those patients, the Week 76 sputum samples must be taken in a window beginning six weeks prior to the scheduled visit date and ending within the Week 84 visit window i.e. within 14 weeks of the scheduled Week 76 visit date.

3.2 **Primary efficacy outcome**

The primary efficacy outcome measure is the proportion of patients with a favourable outcome (as defined below) at Week 76.

Only data from events occurring before the end of the Week 76 window will be included in the primary analysis of the primary efficacy outcome.

Culture results obtained using acidified Ogawa (Kudoh medium) will be used in the primary analysis, unless missing, when results from Löwenstein-Jensen (LJ) media will be used.

A positive culture is defined as at least one colony and a negative culture is defined as absence of growth (no colonies).

Favourable

A patient's outcome will be classified as **favourable** if their last two culture results are negative unless they have previously been classified as unfavourable. These two cultures must be taken on separate visits (on different days); the latest of which being within the Week 76 window.

Patients that don't have a culture result within the Week 76 window because they were unable to produce sputum or their sample was contaminated, will be classified as favourable if their last two cultures before the Week 76 window are negative and they have not previously been classified as unfavourable; such patients will be identified separately in tables.

Participants with no sputum sample available at Week 76 due to Covid-19 restrictions who are not otherwise classified as unfavourable will be considered unfavourable. Sensitivity analyses will reclassify these participants as i) non-assessable and excluded from the primary efficacy analysis, and ii) favourable if they meet the definition of favourable above, with the latest of the 2 negative culture results being within the Week 68 window, and unfavourable otherwise.

Unfavourable

A patient's outcome will be classified as **unfavourable** in Stage 2 if:

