- 1. They are discontinued from their allocated study treatment and subsequently restarted on a different MDR-TB regimen.
- 2. Treatment is extended beyond the scheduled end of treatment for any reason other than making up days when no treatment was given (missed treatment) for a maximum of eight weeks. A maximum of 14 days of extra treatment (irrespective of reason) is acceptable before it is classified as treatment extension.
- 3. They are restarted on any MDR-TB treatment after the scheduled end of treatment, but before 76 weeks after randomisation.
- 4. They change their allocated study treatment for any reason other than the replacement of a single drug.
- 5. Bedaquiline is started where the allocated regimen did not originally contain that drug (Regimen A or B).
- 6. A second line injectable agent is started in Regimen C.
- 7. A drug from the class of nitroimidazoles (delamanid or pretomanid) or linezolid is started.
- 8. They die at any point during treatment or follow-up.
- 9. At least one of their last two culture results, from specimens taken on separate occasions, is positive.
- 10. They do not have a culture result within the Week 76 window.

Starting a single drug other than bedaquiline (in Regimen A or B) or from the class of nitroimidazoles (delamanid or pretomanid) or linezolid (in any regimen) is not considered to be a substantial change to the regimen and therefore does not result in an unfavourable outcome, providing none of the other criteria above are met.

An extension of the intensive phase of treatment in any study arm does not constitute an unfavourable outcome, as long as the extension is in accordance with the algorithms described in Figure 5 and Figure 6 in Section 1.5 for patients on Regimen B, Regimen C, and Regimen D. Similarly, the discontinuation of drugs that are not replaced does not constitute an unfavourable outcome.

These definitions of favourable and unfavourable apply to all four treatment regimens and for analyses of both the mITT, PP and mPP analysis populations.

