The assumption of proportional hazards between the two comparisons will be tested using the proportional hazards test based on the Schoenfeld residuals after fitting the Cox Proportional Hazards models. In the case where there is adequate evidence that the proportional hazard assumptions are violated at the 5% level (i.e. p<0.05), methods where proportional hazards is not a necessary assumption will be used, such as the Wilcoxon test of equality of survivor functions and restricted mean survival time.

Sensitivity analyses will be conducted i) considering different dichotomies of the 5 point scale and ii) assessing the assumption of independent or non-informative censoring (i.e. that the likelihood of an FoR event at the time of censoring is assumed to be the same as for those in whom no censoring occurred) using inverse probability of censoring weights (IPCW)⁸ and multiple imputation(MI)⁹ respectively.

This failure or recurrence analysis will be repeated in subgroups according to baseline characteristics as described in Section 6.3.

7.1.4 Favourable outcome at Week 132

A patient's outcome will be classified as favourable if their last two sputum culture results are negative, unless they have previously been classified as unfavourable. These two sputum results must be from samples taken at separate visits; the latest must be no more than six weeks before their scheduled last efficacy visit (see Section 7.1).

A patient's outcome at their scheduled last efficacy visit will be classified as unfavourable if:

- They are unfavourable at Week 76
- They start any MDR-TB treatment between their Week 76 and scheduled last efficacy visits
- They die between their Week 76 and scheduled last efficacy visits
- At least one of their last two culture results, from specimens taken on separate occasions, is positive.

A patient who does not have a culture result within the window for their scheduled last efficacy visit, having not otherwise been classified as unfavourable, will be regarded as non-assessable if their last two cultures, from specimens taken on separate occasions, are negative. All other patients who do not have a culture result within the window for their scheduled last efficacy visit and do not meet this definition of non-assessable will be classified as unfavourable.

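### A restart of MDR-TB treatment stops counting at 76.0 weeks while other primary-outcome events count to the end of the Week 76 window, so some retreated patients can be classed favourable

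*SAP*

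**What the plan says.** SAP Section 3.2 lists the events that make a Stage 2 outcome unfavourable. Item 3 concerns patients who have passed the scheduled end of treatment: "They are restarted on any MDR-TB treatment after the scheduled end of treatment, but before 76 weeks after randomisation". Protocol Section 11.2.1, item 3, sets the same limit alongside its Stage 1 counterpart: "before 132 weeks after randomisation for Stage 1 and before 76 weeks after randomisation for Stage 2".

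The general data rule in SAP Section 3.2 runs later: "Only data from events occurring before the end of the Week 76 window will be included in the primary analysis". SAP Section 3.1 gives that window, "i.e. from Week 70 to Week 82". For patients whose Week 76 appointment was missed for pandemic reasons, Section 3.1.1 extends it, "ending within the Week 84 visit window i.e. within 14 weeks of the scheduled Week 76 visit date".

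No other item on the list stops at 76.0 weeks. Item 8 reads "They die at any point during treatment or follow-up", and item 9 reads "At least one of their last two culture results, from specimens taken on separate occasions, is positive". Items 5 to 7 (starting bedaquiline in Regimen A or B, an injectable in Regimen C, or a nitroimidazole or linezolid in any regimen) have no date limit of their own.

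The estimand table in SAP Section 3.3 places salvage treatment among the changes handled by a composite strategy. Such a patient is unfavourable under both co-primary estimands, again with no 76-week limit. For the Week 132 outcome, SAP Section 7.1.4 counts patients if "They start any MDR-TB treatment between their Week 76 and scheduled last efficacy visits".

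**The concern.** Item 3 is the general rule for retreatment after a completed course, and it applies whatever drugs are used. Between 76.0 weeks and the end of the window it no longer applies, although cultures and deaths in that period still decide the outcome. A negative sputum obtained on retreatment can then help a patient to qualify as favourable.

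Two things are at stake. First, the definition and the estimand table disagree: the table says that salvage treatment is captured in the composite, and for some restarts inside the window it is not. Second, what remains after 76.0 weeks depends on the drug chosen and on the arm. Protocol Section 11.2.1 explains that linezolid was added to the list in version 11.0 because items 5 and 6 had become unequally likely to occur, so the trial team has already judged this kind of imbalance worth correcting.

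**Working it through.** **Inputs.** Randomisation is day 1 (SAP Section 5.3), so day = 7 × week + 1. The visit table in SAP Section 5.3 gives Week 76 as days 491 to 574 (target 533) and Week 84 as days 575 to 630. SAP Section 2.1 gives planning rates of 80% (B) and 82% (C), a 10-point margin and 172 evaluable patients per arm.

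**1. The plan's window, reproduced.** Week 70: 7 × 70 + 1 = 491. Week 76: 7 × 76 + 1 = 533. Week 82: 7 × 82 + 1 = 575, and the table ends the day before, at 574. Week 90 (76 + 14): 7 × 90 + 1 = 631, and the Week 84 window ends the day before, at 630. The dates agree.

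**2. Length of the gap.** Item 3 covers restarts before day 533.
- Ordinary window: 574 − 533 + 1 = 42 days, half of the 84-day window (574 − 491 + 1 = 84).
- COVID-extended window: 630 − 533 + 1 = 98 days.

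**3. What still counts between day 533 and the end of the window.**

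| Event | Item | Regimen B | Regimen C |
|---|---|---|---|
| MDR-TB restart as such | 3 | no | no |
| Restart with linezolid or a nitroimidazole | 7 | yes | yes |
| Restart with bedaquiline | 5 | yes | no |
| Restart with an injectable | 6 | no | yes |
| Death | 8 | yes | yes |
| A positive among the last two cultures | 9 | yes | yes |

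Items 1 and 4 concern patients who discontinue or change allocated treatment. They do not naturally describe someone who finished it. Regimens B and C last at most 48 weeks with intensive-phase extension, plus up to 8 weeks for missed days (48 + 8 = 56), well before Week 76.

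**4. Routes to a favourable outcome.** The restart must contain no drug caught by items 5 to 7, and the last two cultures must be negative. Examples are:
- a relapse judged on clinical or radiological grounds, with negative cultures;
- an earlier positive, for example at Week 60, followed by negatives at Weeks 68 and 76;
- a COVID-extended patient who was negative at Week 68, restarted after Week 76, and gave a negative sample on retreatment by Week 90;
- a patient whose window sample was contaminated or who could not produce sputum. SAP Section 3.2 classes such a patient as favourable if the last two cultures before the window were negative.

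**5. Size.** One patient in 172 is 100/172 = 0.58 points. The documents give no number of restarts in the gap, so 0 to 3 per arm is an assumption. With d = pB − pC, the unstratified upper 95% limit is d + 1.96 × √[pB(1 − pB)/172 + pC(1 − pC)/172]. The lines below start from the planning rates and show the effect of reclassifying patients as unfavourable under the aligned rule.

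| Reclassified in B / C | d (points) | Upper limit |
|---|---|---|
| 0 / 0 | −2.00 | 6.29 |
| 0 / 1 | −1.42 | 6.92 |
| 0 / 2 | −0.84 | 7.55 |
| 0 / 3 | −0.26 | 8.18 |
| 1 / 1 | −2.00 | 6.38 |
| 2 / 2 | −2.00 | 6.48 |
| 3 / 0 | −3.74 | 4.68 |

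The upper limit stays below 10 in every case.

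**6. Cover elsewhere.** None of sensitivity analyses A to L in SAP Section 6.4 moves the item 3 cut-off.

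**The case against.** The strongest reply is that most late retreatment is caught anyway. Items 5 to 7 run to the end of the window, and protocol Section 11.2.1 expects salvage after bedaquiline to contain linezolid more often than an injectable. Item 9 needs both last cultures to be negative, so one negative on retreatment is not enough. The Week 84 window opens on day 575, after the ordinary Week 76 window closes. A patient restarted for a positive Week 76 culture would therefore need two later negatives, largely from unscheduled visits, by day 574. Protocol Section 9 also discourages restarting without evidence of failure or recurrence. All of this stands, and it makes the gap narrow. It does not close the routes in step 4.

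A reader might infer that retreatment after 76 weeks never counts. The documents do not support that, because items 5 to 7 still apply.

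A reader might also infer that a restart after 76.0 weeks but before a late Week 76 visit escapes the Week 132 outcome too. SAP Section 5.3 says that, from there on, a visit means its window. Section 7.1.4 can then be read as starting at the Week 76 window, which leaves no gap. The wording is at most ambiguous.

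Finally, the 76-week limit is in the protocol as well, with a parallel limit for Stage 1, and the protocol describes the outcome as status at 76 weeks. The limit may therefore have been deliberate. Neither document gives a reason for stopping this one item early, and the estimand table does not follow it.

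**Conclusion.** The point holds in a limited form. Item 3 and the rest of the primary outcome end on different dates, and item 3 does not match the estimand table. Followed literally, a patient retreated between 76.0 weeks and the end of the window can be favourable, provided that no drug in items 5 to 7 is used and the last two cultures are negative. Which restarts escape depends on the drug and the arm.

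The effect is probably small: 0.58 points of one arm's rate per patient at 172 per arm, with few patients expected. Up to three reclassified in one arm would not by itself take the upper limit past 10 points at the planning rates. That rests on the assumed counts and on an unstratified interval, whereas the plan uses a stratified one.

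Each misclassification favours the arm in which it occurs. A reader might infer a bias towards non-inferiority, but the documents give no counts by arm and so no direction for the B minus C difference. They also do not show how item 3 was programmed.

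**What to change.** - **Align the text.** End item 3 at the end of the participant's Week 76 window, including any COVID extension, in SAP Section 3.2 and protocol Section 11.2.1, so that both agree with the estimand table in SAP Section 3.3. If the earlier stop is intended, give the reason and amend the table instead.
- **Apply it as a sensitivity analysis.** SAP version 6.0 describes comparisons already made at the time of the primary analysis (Section 6.1.3), so changing the primary definition now would be post hoc. Keep the primary result, add the aligned rule to the list in Section 6.4, and state how item 3 was programmed.
- **Tabulate.** Show by arm the restarts between Week 76 and the end of the window, with the drugs started and the outcome assigned.
- **Clarify Section 7.1.4.** State that treatment started after Week 76 is counted from the point where item 3 ends, with no gap. This confirms a reading that Section 5.3 already allows.

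The cost is a phrase in two definitions, one sentence in Section 7.1.4, one repeat of an existing analysis and one small table. No new data are needed beyond treatment start dates and drugs, which the existing items already require. A few outcomes may become unfavourable in the sensitivity analysis.
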